## **Purpose:**

Primary purpose: To investigate whether intraoperatively administered morphine improves postoperative analgesia.

Secondary purpose: To investigate whether intraoperatively administered morphine increases opioid related adverse effects.

## **PICO:**

Population: adult patients who have undergone elective laparoscopic cholecystectomy

Intervention: change in anesthesia technique to include an intraoperative dose of morphine

Comparison: A) no morphine = patients operated in the year before the change in anesthesia protocol (June 1st 2022 – May 31st 2023)

B) morphine = patients operated in the year following the change in anesthesia protocol (Jan 1st 2024 – Dec 31st 2024)

Outcomes: Primary: use of rescue analgesia in the postoperative ward

Secondary: pain scores on admittance and discharge from postoperative ward, time from end of surgery to admittance to postoperative ward (surrogate measure for emergence from anesthesia), use of rescue antiemetic treatment in the postoperative ward, time in postoperative ward, use of analgesic and antiemetic treatment in the first 24 hours after discharge from postoperative ward, time in hospital.

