### **Design:**

Retrospective, observational, data from patient records/register based

Investigation site: Hospital of South West Jutland Esbjerg

Population:

2 groups:

- a) No morphine intraoperatively: Patients operated in the year before change in anesthesia protocol
- b) Morphine intraoperatively: Patients operated in the year after change in anesthesia protocol

Inclusion criteria:

- Patient having undergone elective laparoscopic cholecystectomy

Exclusion criteria:

- Age under 21 (because these patients are admitted to a separate ward for children and young adults)
- Patients who are unable to give consent to anesthesia
- Patients who cannot participate in pain-scoring by numerical ranking scale (NRS)
- Patients with chronic pain (characterized by patient receiving regular analgesic treatment and patients with active or previous contact to pain clinic)
- Patients with active or previous substance abuse
- Emergency surgery

Outcomes

Primary:

- Use of rescue analgesia (calculation of total morphine equivalents) in the postoperative ward

Secondary:

- Intraoperative opioid use (calculation of total morphine equivalents)
- Time from end of operation to admittance to postoperative ward (surrogate measure of emergence from anesthesia)
- Pain score at admittance to postoperative ward, scale from 0 to 3\*
- Pain score at discharge from postoperative ward, scale from 0 to 3\*

\*Due to retrospective, register based design we cannot use standard numerical ranking scale (NRS), since local practice is to register pain in intervals of NRS: no pain = 0, light pain = 1-3, moderate pain = 4-6, severe pain = 7-10

- Use of rescue antiemetic treatment in the postoperative ward
- Time in postoperative ward
- Analgesic use in surgical ward during first 24 hours if admitted\*\*
- Use of antiemetic treatment in surgical ward during first 24 hours if admitted\*\*
  - \*\* It is expected that a large proportion of the included patients will be managed as outpatients.
- Total admission time.

Other data collected for statistical analysis:

- Age at operation
- Gender
- ASA-classification
- Co-morbidity
- Height
- Weight
- Smoking habits (smoker/non-smoker)
- Use of alcohol (none, 1-21 units per week, > 21 units per week)
- In-patient/out-patientstatus
- Anesthesia maintenance (intravenous or inhalational)'
- Dose of fentanyl, remifentanil and morphine
- Use of lidocaine
- Postoperative nausea and vomiting (PONV)-prophylaxis
- Use of vasopressor or inotropes

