**Anticipated time schedule:**

2023	Protocol, permissions and generation of data collection tool in Redcap
Feb - Sept 2024	Data collection, no-morphine group
Oct 2024 – April 2025	Data collection, morphine group
April 2025 - ?	Data management, analyses, manuscript, publication

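### Do the 214 days between the two study windows leave the before and after groups undefined?

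*Protocol*

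**What the plan says.** The PICO section gives each group a label followed by dates in parentheses. The comparator is "no morphine = patients operated in the year before the change in anesthesia protocol", with the dates "June 1 st 2022 – May 31 st 2023". The morphine group is "morphine = patients operated in the year following the change in anesthesia protocol", with the dates "Jan 1 st 2024 – Dec 31 st 2024". The intervention is itself described as a "change in anesthesia technique to include an intraoperative dose of morphine".

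The Design section restates the two groups without dates: "No morphine intraoperatively: Patients operated in the year before change in anesthesia protocol" and "Morphine intraoperatively: Patients operated in the year after change in anesthesia protocol".

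No section states when the anesthesia protocol changed, and none mentions a transition or excluded period. The anticipated time schedule places data collection for the no-morphine group in February to September 2024 and for the morphine group in October 2024 to April 2025.

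**The concern.** In an uncontrolled before-after study the calendar window is what places a patient in a group, so its definition matters more than most wording in the protocol. Here a label and a pair of dates define each group, and they appear to disagree. The year before and the year after a single event touch at that event, yet the printed windows are seven months apart.

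Three things could be at stake:

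- Someone working from the undated labels in the Design section might select different patients from someone working from the PICO dates.
- A reader cannot tell whether the omitted months contain untreated patients, treated patients or both, or why the patients nearest the change were left out.
- The gap lengthens the time between the groups, which leaves more room for drift in practice unrelated to morphine.

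**Working it through.** The protocol states no figure for the gap or the overlap, so there is nothing of its own to reproduce. The check is calendar arithmetic on the four dates in the PICO section.

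**Window lengths and gap**

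- No-morphine window: 1 June 2022 to 31 May 2023 = 365 days.
- Morphine window: 1 January to 31 December 2024 = 366 days (leap year).
- Total: 365 + 366 = 731 days.
- Gap, June to December 2023: 30 + 31 + 31 + 30 + 31 + 30 + 31 = 214 days.

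**Labels against dates, assuming a single change date c**

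Take the year before as the twelve months ending the day before c, and the year after as the twelve months starting on c. For c anywhere from 1 June 2023 to 1 January 2024, the days that fall in a label-defined year but outside the printed windows are:

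(c − 1 June 2023) in the no-morphine group + (1 January 2024 − c) in the morphine group = 214.

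| Assumed change date | No-morphine days | Morphine days | Total |
|---|---|---|---|
| 1 June 2023 | 0 | 214 (214/366 = 58%) | 214 |
| 16 September 2023 | 107 (107/365 = 29%) | 107 (107/366 = 29%) | 214 |
| 1 January 2024 | 214 (214/365 = 59%) | 0 | 214 |

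The total is the same for every date in the gap, and 214/731 = 29.3%. Counting instead the printed days that fall outside the label-defined years also gives 214 for every such date. For change dates outside the gap that count is larger: 216 days for 31 May 2023 and 276 days for 1 February 2024. So 29% is the minimum under a single change date. The constant total shows that the figure is simply the length of the gap divided by the length of the windows. These are shares of days; they become shares of patients only if operating volume was even.

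**Labels against dates, assuming a phased change**

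Suppose the change began on 1 June 2023 and was complete by 31 December 2023. The year before it began is then 1 June 2022 to 31 May 2023, and the year after it was complete is 1 January to 31 December 2024. Both match the printed windows exactly: 0 of 731 days disagree. The protocol does not say that this happened.

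**Separation in time**

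- Window starts: 365 + 214 = 579 days apart. Midpoints: 579 + (366 − 365)/2 = 579.5 days, about 19.0 months.
- Adjoining years of 365 and 366 days: midpoints 365.5 days apart, about 12.0 months.
- Attributable to the gap: 579.5 − 365.5 = 214 days, about 7.0 months.

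**Timetable**

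Morphine-group collection runs to April 2025, after the printed window closes on 31 December 2024. It begins on 1 October 2024 with 92 days of that window still to come (31 + 30 + 31), which works if records are taken as they accrue. The schedule therefore fits the printed windows. It also fits adjoining years around 1 June 2023 or 1 January 2024, so it neither confirms nor contradicts them.

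**The case for a change.** The strongest case for a change is that cohort definition belongs in the protocol, and that this protocol gives two definitions which no single change date can reconcile. The inclusion and exclusion criteria contain neither a date nor a requirement that morphine was given, so the window carries the whole assignment. A phased introduction is plausible but unstated, and nothing says that the dates override the labels.

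What stands is that the protocol should ideally have said when the change took place and why seven months were left out. A reader of the eventual report will want to know.

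The step from there to two competing sets of patients does not stand. The labels in the Design section cannot be used to pull records, because they need a change date that the protocol never supplies. Anyone extracting data has to go to the PICO section, where each label is followed at once by its dates. In ordinary reading the dates specify the label. Selecting other patients would take a change date from outside the document and a decision to override the printed ones.

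A patient's actual exposure would also be visible. The Design section lists the morphine dose among the data collected, so a patient whose treatment did not match the period would show up.

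The extra seven months of separation are real, but they come with a trade-off. Adjoining windows would cut the separation from 19 to 12 months by exchanging 214 days of records for another 214, and could bring in patients treated while the change was still being taken up. Neither choice is clearly better on the information in the protocol.

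**Conclusion.** The observation is accurate and the consequence is small. The windows are 214 days apart, the reason is not given, and the labels are loose. The 29% mismatch holds only if the change fell on one day and the labels mean the twelve months touching that day; under a change phased over the gap it is zero.

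Following the protocol as printed gives two well-defined groups, each spanning twelve whole calendar months. The effect of the gap on the treatment comparison cannot be calculated, because the protocol gives no sample size, standard deviation or time trend, and its direction is unknown.

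This conclusion rests on the PICO dates being the intended ones, and nothing in the protocol suggests otherwise. On that basis the missing explanation is a gap in wording that analysts would fill correctly from the printed dates. Supplying it would change neither the cohorts nor the analysis.

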## **Background:**

Pain following laparoscopic cholecystectomy is complex and stems from several stimuli: e.g. skin-incisions, abdominal distention due to pneumoperitoneum and irritation of the phrenic nerve. Postoperative pain continues to be a problem despite years of focus on the issue as well as increased use of laparoscopic and minimally invasive, surgical technique. This holds true for laparoscopic cholecystectomy as well. Some investigators report that as much as 50-70% of patients experience moderate to intensive pain postoperatively. It is well known that postoperative pain causes increased morbidity and is a primary cause of prolonged length of hospital stay. Multimodal analgesic approach is recommended for this type of surgery. Because use of opioids frequently cause adverse effects an opioid-sparing approach is recommended. However, non-opioid analgesia also has the potential for adverse effects. Even if it is possible to perform opioid-free anesthesia knowledge and evidence is still sparse, and peri- and postoperative opioid rescue analgesia is often necessary.

We hypothesize, that multimodal analgesia including a perioperative dose of morphine (0,1 mg/kg) given 20 minutes after start of surgery will have beneficial effect on postoperative pain without causing significant increase in opioid related adverse effects.

### **Design:**

Retrospective, observational, data from patient records/register based

Investigation site: Hospital of South West Jutland Esbjerg

Population:

2 groups:

- a) No morphine intraoperatively: Patients operated in the year before change in anesthesia protocol
- b) Morphine intraoperatively: Patients operated in the year after change in anesthesia protocol

Inclusion criteria:

- Patient having undergone elective laparoscopic cholecystectomy

Exclusion criteria:

- Age under 21 (because these patients are admitted to a separate ward for children and young adults)
- Patients who are unable to give consent to anesthesia
- Patients who cannot participate in pain-scoring by numerical ranking scale (NRS)
- Patients with chronic pain (characterized by patient receiving regular analgesic treatment and patients with active or previous contact to pain clinic)
- Patients with active or previous substance abuse
- Emergency surgery

Outcomes

Primary:

- Use of rescue analgesia (calculation of total morphine equivalents) in the postoperative ward

Secondary:

- Intraoperative opioid use (calculation of total morphine equivalents)
- Time from end of operation to admittance to postoperative ward (surrogate measure of emergence from anesthesia)
- Pain score at admittance to postoperative ward, scale from 0 to 3\*
- Pain score at discharge from postoperative ward, scale from 0 to 3\*

\*Due to retrospective, register based design we cannot use standard numerical ranking scale (NRS), since local practice is to register pain in intervals of NRS: no pain = 0, light pain = 1-3, moderate pain = 4-6, severe pain = 7-10

- Use of rescue antiemetic treatment in the postoperative ward
- Time in postoperative ward
- Analgesic use in surgical ward during first 24 hours if admitted\*\*
- Use of antiemetic treatment in surgical ward during first 24 hours if admitted\*\*
  - \*\* It is expected that a large proportion of the included patients will be managed as outpatients.
- Total admission time.

Other data collected for statistical analysis:

- Age at operation
- Gender
- ASA-classification
- Co-morbidity
- Height
- Weight
- Smoking habits (smoker/non-smoker)
- Use of alcohol (none, 1-21 units per week, > 21 units per week)
- In-patient/out-patientstatus
- Anesthesia maintenance (intravenous or inhalational)'
- Dose of fentanyl, remifentanil and morphine
- Use of lidocaine
- Postoperative nausea and vomiting (PONV)-prophylaxis
- Use of vasopressor or inotropes
- Paracetamol and/or NSAIDs given preoperatively or intraoperatively
- Pre- and postoperative C-reactive protein (CRP)-values, if taken

Analyses:

- Per protocol
  - o a) No-morphine vs b) Morphine
  - o T-test, statistical difference in:
    - Analgesic use in postoperative ward (primary)
    - Intraoperative analgesic use
    - Pain scores in postoperative ward
    - Time for end of surgery to admittance to postoperative ward

- Use of rescue antiemetic drugs in postoperative ward
- Time in postoperative ward
- Use of opioid analgesia and antiemetic drugs in surgical ward
- Time in hospital
- If necessary and possible logistic regression analyses.

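### Minor: the tested secondary outcome of intraoperative opioid use includes the intervention morphine, so it cannot show whether other theatre opioid changed

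*Protocol*

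**What the plan says.** The PICO section of the Protocol defines the intervention as a "change in anesthesia technique to include an intraoperative dose of morphine". The two groups are patients operated on in the year before and the year after that change. The hypothesis in the Background section describes "multimodal analgesia including a perioperative dose of morphine (0,1 mg/kg) given 20 minutes after start of surgery", so the dose falls within the intraoperative period.

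Among the secondary outcomes in the Design section is "Intraoperative opioid use (calculation of total morphine equivalents". No exclusion of the intervention morphine is stated. The Analyses list then names "Intraoperative analgesic use" among the items for a t-test between the no-morphine and morphine groups, per protocol.

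The primary outcome is "Use of rescue analgesia (calculation of total morphine equivalents) in the postoperative ward", which does not count theatre opioid. The only later opioid comparison is "Use of opioid analgesia and antiemetic drugs in surgical ward". Component doses are collected, as "Dose of fentanyl, remifentanil and morphine", under the other data for statistical analysis. No listed comparison uses them separately.

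The outcome is absent from the PICO list, whose secondary outcomes begin "Secondary: pain scores on admittance and discharge from postoperative ward, time from end of surgery to admittance to postoperative ward". It is called opioid use in the outcome list and analgesic use in the Analyses list.

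**The concern.** The drug that defines the groups is also a component of an outcome compared between them. Part of the difference is therefore fixed by the design and says nothing about how patients responded or how anesthetists otherwise dosed.

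A significant rise could be the intervention dose and nothing more. A null result could conceal a real fall in fentanyl or remifentanil of about the same size as the added morphine. The t-test as listed cannot tell these situations apart, and no other listed comparison does so. At stake is the reading of one secondary result.

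**Working it through.** **Inputs from the Protocol.** Dose 0.1 mg/kg (Background). Outcome: total intraoperative morphine equivalents (Design). Comparison: t-test between groups (Analyses). The Protocol gives no sample size, power, standard deviation, expected effect, body weights or conversion factors, so there is no stated figure to reproduce.

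**Assumptions.** Body weights of 60, 80 and 100 kg; every patient in the morphine group receives the full dose; no theatre morphine in the comparison year. If only a fraction f of patients received the dose, the built-in part becomes f × D.

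**Step 1: the built-in part.** D = 0.1 × weight.
- 60 kg: 0.1 × 60 = 6 mg
- 80 kg: 0.1 × 80 = 8 mg
- 100 kg: 0.1 × 100 = 10 mg

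**Step 2: what the listed comparison measures.** Let a be the fall in other theatre opioid, in mg morphine equivalents. The listed difference (morphine minus no morphine) is D − a. At 80 kg:

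| Fall in other theatre opioid, a (mg) | Listed difference, 8 − a (mg) |
|---|---|
| 0 | +8 |
| 3 | +5 |
| 8 | 0 |
| 10 | −2 |

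The sign and size of the listed result therefore do not reveal a.

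**Step 3: would a t-test pick up the dose alone?** This is an illustration only, with assumed standard deviations and group sizes and two-sided alpha 0.05. For a built-in 8 mg difference the chance of p < 0.05 is 0.98 at SD 10 mg and 50 per group, 0.52 at SD 20 mg and 50 per group, and 0.81 at SD 20 mg and 100 per group. Steps 1 and 2 do not depend on these values.

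**Step 4: after removing morphine from the tested variable.** The built-in part goes from D to 0, and the difference is −a, the change in fentanyl plus remifentanil.

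**Step 5: opioid up to ward discharge (supporting description only).** Let w be the fall in postoperative-ward opioid. The theatre-plus-ward difference is D − a − w. At 80 kg with a = 0, ward falls of 2, 4 and 8 mg give 8 − 2 = +6, 8 − 4 = +4 and 8 − 8 = 0 mg. With a = 0, the total falls only once w exceeds 6, 8 or 10 mg at the three assumed weights.

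**The case against.** The strongest reply is that the Protocol never says this outcome measures an effect on other theatre opioid. Total theatre opioid, intervention included, is a legitimate description of exposure, and it is relevant to the secondary purpose of opioid-related adverse effects. That stands, and is why the total should be kept. It does not rescue the t-test, which examines a difference that partly defines the groups.

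It can also be said that inclusion of the intervention morphine is inferred, that the component doses are already marked for analysis, and that an unseen SAP may break the total down. The inference is fair to point out, but a total with no stated exclusion reads plainly. The outcome and its test are written into the Protocol, so a SAP that tested something else would depart from it.

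A third reply is that the arithmetic only restates that the total equals the dose plus the rest, and that without baseline theatre use nobody can say whether 6 to 10 mg is a large share of it. This is correct. The figures show the built-in amount, not its relative importance.

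Finally, a between-year difference in fentanyl plus remifentanil could reflect other parts of the changed technique or calendar time. This also stands. The replacement comparison removes the built-in component but does not attribute what remains to morphine.

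**Conclusion.** The point holds as a minor one. As written, the tested secondary outcome is the intervention dose (6, 8 or 10 mg at assumed weights of 60, 80 or 100 kg, if fully given) plus any change in other theatre opioid, and it cannot show whether the latter changed. This rests on reading the total as including the intervention morphine, which nothing in the Protocol contradicts.

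Two stronger readings are tempting but unsupported. A reader might infer that the primary outcome is compromised because it leaves out theatre opioid. It is not: it counts ward use only, does not contain the intervention dose, and fits the stated purpose of assessing postoperative analgesia. A reader might also infer that the Protocol claims, or needs to prove, lower opioid use overall, so that a fall in ward use must first be offset against the theatre dose. The Purpose section names postoperative analgesia and opioid-related adverse effects, and opioid sparing appears only as background. The theatre-plus-ward total is therefore useful context, not a condition on how the primary result may be worded.

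**What to change.** 1. Keep total intraoperative morphine equivalents, reported descriptively by year, and remove it from the t-test list.
2. Make the tested comparison intraoperative fentanyl plus remifentanil, in morphine equivalents, with the same stated conversion factors in both years.
3. Report any theatre morphine in each year separately. Leaving all morphine out of the tested variable avoids having to separate the intervention dose from other theatre morphine, which is possible only if doses were recorded individually.
4. State that the result is a between-year difference that may also reflect other changes in practice.
5. Optionally, report the per-patient theatre-plus-postoperative-ward opioid total with its 95% CI beside the primary result, as a supporting description that excludes surgical-ward opioid.
6. Editorial: use one name for the outcome in the outcome list and the Analyses list, and add it to the PICO outcomes.

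The cost is one more derived variable (two with the optional total) and a few lines of text. No new data are needed, since the component doses and ward use are already collected. The downside is dependence on the conversion factors.

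### Surgical-ward analgesic and antiemetic use is compared only among admitted patients, a subset that may depend on the morphine given, while the admitted proportion is not an outcome and PICO states no such limit

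*Protocol*

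**What the plan says.** The outcome appears in three places in the protocol, with three different scopes.

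- **PICO, Outcomes:** "use of analgesic and antiemetic treatment in the first 24 hours after discharge from postoperative ward". No condition on admission is given.
- **Design, Secondary outcomes:** "Analgesic use in surgical ward during first 24 hours if admitted" and "Use of antiemetic treatment in surgical ward during first 24 hours if admitted". The footnote to both adds: "It is expected that a large proportion of the included patients will be managed as outpatients".
- **Analyses:** in the list of comparisons that opens with "T-test, statistical difference in", the item reads "Use of opioid analgesia and antiemetic drugs in surgical ward". It repeats neither the admission condition nor the 24-hour window, and it names opioids where Design names analgesics.

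"In-patient/out-patientstatus" is recorded under the other data collected for statistical analysis. It is not an outcome, and no comparison of it is listed. Total admission time is a secondary outcome, and time in hospital is in the list of comparisons.

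The protocol gives no admission rate and no reasons for admission. It does not say whether in-patient status is decided before surgery or on the postoperative course.

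**The concern.** According to the Background, morphine is given 20 minutes after the start of surgery. An overnight stay decided later is a post-exposure event. The Background supplies two routes from exposure to that event: it says that "Because use of opioids frequently cause adverse effects an opioid-sparing approach is recommended", and it names postoperative pain as a main reason for longer hospital stays. Morphine could therefore add admissions through nausea or sedation, or remove admissions through better pain relief. In either case the admitted patients of the two periods would be different kinds of patient, even if the full groups were alike.

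Two purposes are touched. Ward analgesic use bears on the primary purpose, postoperative analgesia. Ward antiemetic use bears on the secondary purpose, opioid-related adverse effects. A lower mean among admitted patients could reflect a changed case mix rather than less need, and a reader who sees only that mean could not tell which. Because the three places differ in scope, it is also unclear whether a patient sent home counts as zero, as missing or as outside the analysis.

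**Working it through.** The protocol gives no sample size, effect size or admission rate, so there is no figure of its own to reproduce. Every rate and mean below is an assumption, used to show what the restriction can do.

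**Formulas.** Let a be the admitted share without morphine, with mean ward opioid 10 mg. Let d be the extra share admitted with morphine, with mean m, and let morphine change nobody else. Patients sent home have no ward use.

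- Admitted-only mean with morphine = (a × 10 + d × m) / (a + d)
- Mean per operated patient = a × 10 without morphine, and a × 10 + d × m with morphine

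**Single example: a = 0.20, d = 0.05, m = 4 mg.**

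- Admitted only: (0.20 × 10 + 0.05 × 4) / 0.25 = 2.2 / 0.25 = 8.8 mg, against 10 mg: a fall of 12%.
- Per operated patient: 2.2 mg against 2.0 mg: a rise of 10%.

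**Range.** The relative fall is d(10 − m) / [10(a + d)]. The relative rise is d × m / (10a).

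| Baseline admitted | Extra points | m (mg) | Admitted-only fall | Per-patient rise |
|---|---|---|---|---|
| 20% | 5 | 2 | 16.0% | 5.0% |
| 20% | 5 | 6 | 8.0% | 15.0% |
| 20% | 10 | 2 | 26.7% | 10.0% |
| 20% | 10 | 6 | 13.3% | 30.0% |
| 30% | 5 | 2 | 11.4% | 3.3% |
| 30% | 5 | 6 | 5.7% | 10.0% |
| 30% | 10 | 2 | 20.0% | 6.7% |
| 30% | 10 | 6 | 10.0% | 20.0% |

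The fall runs from 5.7% to 26.7% and the rise from 3.3% to 30%. The signs are opposite at every corner.

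**The opposite direction.** Suppose 12% are admitted with mild pain (5 mg) and 8% with severe pain (15 mg). The control mean is (0.6 + 1.2) / 0.20 = 9.00 mg. Morphine cuts use by 10% and averts 40% of the mild-pain admissions.

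- Admitted only: (0.072 × 4.5 + 0.08 × 13.5) / 0.152 = 1.404 / 0.152 = 9.24 mg, a rise of 0.24 mg.
- Per operated patient: 1.404 − 1.800 = −0.40 mg.

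Here a real benefit looks like harm. With only 20% of mild-pain admissions averted, both differences are negative (−0.41 and −0.29 mg), so there is no reversal.

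**Antiemetics.** Suppose 20% are admitted at 1.00 dose each. Morphine raises need by 10% and adds admissions at 0.66 doses each.

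- 5 extra points: (0.22 + 0.033) / 0.25 = 1.01 doses. The sign is kept, but the 10% harm has almost vanished.
- 10 extra points: (0.22 + 0.066) / 0.30 = 0.95 doses, a fall, while use per operated patient rises by 0.286 − 0.200 = 0.086 doses.

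**No shift in admission.** With 25% admitted in both groups, a mean of 9.00 mg and 10% less use, the differences are −0.90 mg admitted only and −0.23 mg per operated patient. The signs agree. The problem arises only when the admitted share or its make-up moves.

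**The case against.** **The mechanism is not documented.** The protocol nowhere says that postoperative nausea, sedation or pain decides admission. In-patient status is listed alongside patient and anaesthetic characteristics, which is compatible with planned status. If it is always set before surgery, morphine cannot change the subset. This stands as a condition on the point. The protocol does not settle it either way.

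**Extra admissions would not go unseen.** A reader might infer that the plan never tests this harm. That goes too far: total admission time carries no admission condition and would partly reflect extra stays. Rescue antiemetics and time in the postoperative ward also address adverse effects without the restriction. What is absent is the admitted proportion as a result in its own right.

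**PICO is a summary.** It is silent on the population rather than explicit that all patients count, and it is less detailed than Design elsewhere too. Nor does the footnote say that most patients go home; it gives no figure beyond a large proportion. The mismatch is real, but it is a summary lacking a limit rather than two worked-out rival definitions.

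**The restriction has a practical reason, and the alternative has flaws.** Home use is probably not in the records. Counting patients sent home as zero mixes place of care with analgesic need: a dose moved from home to ward would register as an increase. Any change in day-surgery practice between 2022–23 and 2024 would feed straight into it. This stands, and it is why the zero-filled measure is offered only as supportive.

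**An SAP might say more.** It might, but the restriction itself is fixed in the protocol.

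**Conclusion.** The point holds in a limited form. The protocol compares ward analgesic and antiemetic use in subsets defined by admission, does not list the admitted proportion as an outcome or comparison, and states the outcome with different scope in PICO, Design and Analyses. If admission is decided after the morphine is given, the comparison can be biased in either direction. Under the assumed figures, a 6–27% fall among the admitted can coexist with a 3–30% rise per operated patient, and other assumed figures produce the reverse.

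It is tempting to conclude that the comparison will reverse sign, or that it will favour morphine. The documents support neither. They give no admission rates or reasons, so neither size nor direction can be fixed, and if the admitted share and its make-up do not change the sign is preserved. Confidence is high for the mismatch in wording and conditional for the bias. Only secondary outcomes are involved; rescue analgesia in the postoperative ward, the primary outcome, is untouched.

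**What to change.** 1. Add admission to the surgical ward (yes/no, planned versus unplanned where the record shows it) as a secondary outcome, compared between the groups in all operated patients. The in-patient/out-patient status already collected supplies the yes/no part.
2. Label the admitted-only comparisons of ward analgesic and antiemetic use descriptive, and report them beside the admitted proportion.
3. Use one definition in PICO, Design and Analyses, covering the population, the 24-hour window, and whether all analgesics or only opioids are counted.
4. Optionally, as a supportive analysis, compare opioid and antiemetic use in hospital during the first 24 hours after the postoperative ward in all operated patients, with zero for those sent home, and label it in-hospital use.
5. State as limitations that home use is unknown, and that both admission and in-hospital use also reflect any change in day-surgery practice between the two periods.

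The cost is some wording and one added comparison. Separating planned from unplanned stays may need one further item from the record. This is a cheap improvement.
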